⁷ Disease activity assessment to be performed by the Investigator based on BCVA and/or one or more anatomical parameters detected by SD-OCT among IRF, SRF, sub-RPE fluid, hemorrhage and CRT, and/or OCTA parameters and/or 3-field CFP, as per clinical practice. Of note, only which of these functional and/or anatomical parameters the Investigator considered to assess disease activity will be recorded in the eCRF.

⁸ Treatment according to Investigator's decision on treatment regimen (q12w or q8w) based on disease activity assessment.

[REDACTED]

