12.4.2 Statistical model, hypothesis, and method of analysis

To test whether the above-mentioned anatomical parameters are predictors of response to brolucizumab in terms of fluid resolution and stable q12w regimen, participants within the Safety Set are to be divided in:

- q12w fluid-free participants, defined as participants who have maintained a stable q12w regimen up to Week 48 and are devoid of IRF and SRF at Week 48
- not q12w fluid-free participants, defined as participants who present IRF *or* SRF at Week 48 *or* have been on a q8w regimen at any time during the study *or* have dropped out at any time after Baseline

A Recursive Partitioning and Amalgamation (RECPAM) classification-tree analysis will be used to evaluate interactions between imaging measurements assessed by OCT, OCTA, FA, ICGA and CFP and to identify distinct and homogeneous subgroups of participants in terms of q12w fluid-free participants at Week 48.

This tree-based method integrates the advantages of main effects logistic regression and tree-growing techniques. At each partitioning step, the method chooses the covariate and its best binary split to maximize the difference in the outcome of interest. The algorithm stops when user-defined conditions (stopping rules) are met. To obtain more robust and stable splits, a permutation approach will be adopted to choose the best splitting variable. Global and local adjustment for possible confounders will be accounted for. Global variables will adjust the tree structure iteratively and add global coefficients to the model. Local variables will add different adjustment terms for any terminal node in a tree.

The RECPAM construction proceeds in the following three steps:

Step 1: Construction of a large tree.

Starting from the Safety Set (i.e. root node), the maximum dissimilarity between *q12w fluid-free patients vs non q12w fluid-free patients* for the Split Defining Statement (SDS) family (i.e. predictors variable) will be searched. This will identify the first branch of the tree and the corresponding tree. The same search will be performed recursively on the descendants of the root node, until a minimum node size specified by the user is reached. This defines the leaves of the larger tree.

Step 2: Pruning of the large tree and selection of the honest tree.

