Based on the study protocol, the primary endpoint should be analyzed according to Recursive Partitioning and Amalgamation (RECPAM) classification-tree analysis followed by multivariable logistic regression model. The RECPAM procedure was specified to evaluate interactions between imaging measurements assessed by OCT, OCTA, FA, ICGA and CFP and to identify distinct and homogeneous subgroups of participants in terms of q12w fluid-free participants at Week 48. This procedure should also have the aim to select the variables to be included in the multivariable logistic regression model and how to include them (for continuous, a threshold is identified during RECPAM). Based on data analyzed for the planned interim analysis, the image's grading of SD-OCT and mainly OCTA was affected by many ungradable values due to image's quality or due to pathology providing a great number of missing data that in RECPAM procedure cannot be managed. Moreover, the initial planned number of 263 enrolled patients wasn't reached, and the final number of 122 enrolled patient is too small for this type of the analysis. For these reasons, the RECPAM procedure will not be performed and in section 6.3.1 a different method to consider these variables in the multivariable logistic regression model and to choose them will be planned and explained. Moreover, the primary outcome will be considered as 'failure' also for patients who discontinued treatment during the study since for these patients the maintenance of a stable q12w regimen assigned at Week 16 up to Week 48 can not be observed and, thus, also these cases, will be considered as intercurrent event.

Moreover, in the primary analysis OCTA assessments planned in the study protocol will not be considered since based on interim analysis, it was observed that for these parameters most values will be missing.

| | |
|--|----------------------------------|
| | Statistical Analysis Plan |
| | Sponsor: Novartis |

Protocol: CRTH258AIT04

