6.3. Efficacy Evaluation

6.3.1. Primary efficacy analysis

Definition of primary endpoint

The primary aim of the study is to assess which early anatomical parameters measured by multimodal imaging at each visit from Baseline to Week 16, predict in brolucizumab-treated participants with wAMD the q12w fluid-free response at Week 48.

The primary estimand of the study is to identify the q12w fluid-free predictive factors.

Patient will be classified as follows for the outcome of interest:

- **q12w fluid-free:** patients completing the treatment and the study maintaining a stable q12w regimen assigned at Week 16 up to Week 48 and without the presence of IRF and SRF at Week 48 according to SD-OCT grading.
- **not q12w fluid-free:**
 - patient who completes the treatment and the study with the presence of IRF or the presence of SRF at Week 48 according to SD-OCT grading;
 - patient who followed the q8w regimen of treatment at any time during the study (considering also who started with q12w regimen but then due to disease activity shifted to q8w regimen);
 - patient who discontinued treatment at any time after baseline since also the discontinuation from the treatment can be considered as intercurrent event and according to data handling rules should be considered as 'failure'.
 - patient who dropped out at any time after baseline since the discontinuation from the study is considered as intercurrent event and according to data handling rules should be considered as 'failure'.

The following qualitative and quantitative anatomical parameters measured by FA, ICGA, CFP and SD-OCT will be considered as potential predictive factors in the statistical model and, when measured at more than one timepoint, categories variables based on their changes between baseline and Week 16 will be created as described below:

| | |
|--|---|
| | Statistical Analysis Plan |
| | Sponsor: Novartis Protocol: CRTH258AIT04 |

| Variable | Timing of data collection | Source | Categories used in the model | Reference value for the model |
|----------------------------------|---|--|--|-------------------------------|
| Type of predominant CNV lesion | Screening | CRC grading based on SD-OCT, FA, ICGA and CFP at Screening | Type I, Type II, Type III, PCV, UNG/P or UNG/Q. Of note, Type I and PCV will be considered as unique category while UNG/P and UNG/Q will be considered as missing data. | Type I + PCV |

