NA=Not Applicable; CNV=Choroidal Neovascularization; UNG/P=Ungradable due to pathology; UNG/Q=Ungradable due to quality SHRM=Subretinal hyper reflective materia; ORT=Outer retinal tubulation; ELM=External Limiting Membrane; CST=Center Subfield Thickness; PED=Pigment Epithelial Detachment.

Of note, for each variable 'Missing' values can be present in case that images are collected but not graded by Central Reading Center (CRC) since they are collected by means of a not certificated instrument.

| | |
|--|----------------------------------|
| | Statistical Analysis Plan |
| | Sponsor: Novartis |
| | Protocol: CRTH258AIT04 |

Analysis methodology

Firstly, the proportion of patients with and without q12w fluid-free will be provided and then a descriptive summary table by q12w fluid-free and not q12w fluid-free will be provided for each variables described in table above.

A logistic models will be performed for each one of the variables listed above considering as outcome the patients' classification in q12w fluid-free and not q12w fluid-free.

Multivariable logistic model will be performed considering as outcome the patients' classification in q12w fluid-free and not q12w fluid-free and as covariates all the variables with $p<0.10$ in the previous analysis. Results of logistic models will be presented in terms of beta coefficient and standard error, Odds Ratio and relative 95% Confidence interval and p-value.

All these analyses will be performed on Safety population.

Data handling rules

In case of patients who dropped out at any time after baseline, the primary outcome cannot be evaluated since the patient status related to treatment regimen and presence of IRF o SRF at Week 48 are not observed. The dropped-out patients constitute intercurrent event and they will be considered a not q12w fluid-free at Week 48. Similarly, in case of patients who discontinued the treatment at any time after baseline, the primary outcome cannot be totally evaluated since the patient treatment regimen at q12w cannot be observed until Week 48. The patients who discontinued treatment constitute intercurrent event and they will be considered a not q12w fluid-free at Week 48.

Sensitivity of primary analysis

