- 1) To investigate the robustness of the primary analysis with respect to a potential selection bias due to dropouts, a weighted multivariable logistic model will be applied to provide a robust inferential procedure for the analysis of predictors of patients' responses in presence of missingness. Since excluding participants because of missing values could introduce a selection bias, in order to restore the complete-case analysis to its original sample representation, each complete participant will be weighted for the inverse of his/her missingness probability. Firstly, the missingness probability will be estimated by means of a multivariable logistic model in which the outcome variable will be the drop-out status (i.e., 1=patient drop-out; 0=patient who complete the study) and the covariates included will be the following baseline variables: age, sex, time from wAMD diagnosis in study eye to Informed consent (months), type of predominant CNV lesion, CST, BCVA EDTRS score. Secondly, the weighted multivariable logistic regression with the same covariate selected for the multivariable model

| | |
|--|----------------------------------|
| | Statistical Analysis Plan |
| | Sponsor: Novartis |
| | Protocol: CRTH258AIT04 |

previously described will be performed using the inverse missingness probability as weight. Of note, only patients with no missing data for each covariate included in the model can be considered in this analysis.

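### The SAP drops RECPAM without saying what becomes of the protocol's confounder adjustment, so the imaging odds ratios cannot show whether a marker adds to baseline BCVA and age

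*Protocol*

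**What the plan says.** **Protocol.** Section 12.4.2 describes a RECPAM classification tree followed by a multivariable logistic regression. For the tree it says "Global and local adjustment for possible confounders will be accounted for", and explains part of the mechanism: "Global variables will adjust the tree structure iteratively and add global coefficients to the model". Local variables add adjustment terms to each terminal node. No confounder is named. The logistic regression that follows is described in terms of imaging variables and the cut-offs found by the tree.

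**SAP, declared changes.** Section 1.1 cites ungradable images and the final enrolment of 122, and concludes: "For these reasons, the RECPAM procedure will not be performed". It describes RECPAM's purpose as examining interactions, finding subgroups, and choosing variables and thresholds. It promises "a different method to consider these variables in the multivariable logistic regression model and to choose them will be planned and explained". Confounders are not mentioned.

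**SAP, replacement model.** Section 6.3.1 introduces its candidates with "The following qualitative and quantitative anatomical parameters measured by FA, ICGA, CFP and SD-OCT will be considered as potential predictive factors". The table lists seven: predominant CNV lesion type, sub-RPE fluid, SHRM, ORT, ELM integrity loss, type of PED and percentage change in CST. Each is fitted alone, and the multivariable model takes "as covariates all the variables with $p<0.10$ in the previous analysis". No covariate is forced in.

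**SAP, drop-out weights.** The sensitivity analysis in Section 6.3.1 models drop-out on "age, sex, time from wAMD diagnosis in study eye to Informed consent (months), type of predominant CNV lesion, CST, BCVA EDTRS score". The weighted outcome model then keeps the covariates already selected for the main model.

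**Outcome.** Any time on q8w makes a patient a failure (protocol 12.4.2, SAP 6.3.1). Regimen follows the investigator's assessment of disease activity. Protocol Table 8-1, footnote 7, says: "Disease activity assessment to be performed by the Investigator based on BCVA and/or one or more anatomical parameters detected by SD-OCT", with OCTA parameters and CFP as further options.

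**The concern.** Adjustment was part of the protocol's primary method. The SAP removes the procedure that contained it and neither replaces nor waives the adjustment, although Section 1.1 is otherwise detailed about changes (PED volume, OCTA, LOCF, analysis set, HADS prevalence). As planned, no outcome model, main or sensitivity, contains a clinical covariate.

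The stated purpose is to see whether early imaging can support the choice between q12w and q8w. The physician making that choice already knows the patient's age and letter score. If a marker's odds ratio largely restates baseline vision, the marker is still associated with response but gives the physician little that is new. The planned analysis cannot separate these two cases.

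**Working it through.** **1. The plan's own figures.** The planned size uses n = 1.96² × p(1−p) / (w/2)². With p = 0.56 and w = 0.12 this gives 262.9, rounded up to 263, as stated. At N = 122 and p = 0.50 the width is 2 × 1.96 × √(0.25/122) = 17.74%, also as stated. The limit of 12 covariates matches one per 10 patients in the smaller outcome class: 263 × 0.44 / 10 = 11.6.

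**2. The same rule at N = 122.** The smaller class is 122 × 0.44 = 54 patients at 56% responders, 122 × 0.46 = 56 at 46%, and 61 at 50%. The rule therefore allows about 5 to 6 terms.

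**3. What the SAP model could need.** Lesion type has three usable categories (2 df), the five four-level variables need 3 df each (15), and CST needs 1: 18 df if all pass the screen. That is 54/18 = 3.0 to 56/18 = 3.1 patients per df over the 46% to 56% range. Adding linear BCVA and age gives 20 df, or 2.7 to 2.8 per df.

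**4. Is adjustment present anywhere?** Age and BCVA appear in one model linked to the primary endpoint, the drop-out model. They affect the weights only; the marker odds ratios are not conditional on them. The regimen-choice model in SAP 6.3.2.5 uses the categories of parameters the investigator relied on, not BCVA values, and contains no marker from the primary analysis.

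**5. Illustrative size.** The documents give no association between BCVA and outcome or between BCVA and any marker, so these inputs are assumptions:
- binary marker, 50% prevalence, 61 patients per group
- conditional odds ratio of 1 for the marker
- success odds ratio 1.3 to 2.0 per SD of baseline BCVA
- marker-positive eyes 0.5 to 1.0 SD worse
- 50% responders overall

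The success probability was averaged over a normal BCVA distribution in each marker group, and the unadjusted odds ratio taken from the two averages.

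| OR per SD | Difference (SD) | Success, marker + / − | Unadjusted OR |
|---|---|---|---|
| 1.3 | 0.5 | 48.4% / 51.6% | 0.88 |
| 1.3 | 1.0 | 46.8% / 53.2% | 0.77 |
| 2.0 | 0.5 | 46.1% / 53.9% | 0.73 |
| 2.0 | 1.0 | 42.2% / 57.8% | 0.54 (0.535) |

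The standard error of the log odds ratio is about √(4/61 + 4/61) = 0.36 (0.37 in the last row). The shifts are |ln 0.879| / 0.36 = 0.129/0.36 = 0.4 SE and |ln 0.535| / 0.37 = 0.625/0.37 = 1.7 SE. Such a marker would pass the p<0.10 screen about 12% to 52% of the time, against 10% if it were unrelated to outcome. Response rates of 46% or 56% leave the odds ratios unchanged to two decimals.

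For a contrast with 10% to 20% prevalence, more like some of the SAP's four-level change categories, the SE is about 0.60 to 0.45, and the same log-odds shifts are about 0.129/0.60 = 0.2 to 0.625/0.45 = 1.4 SE.

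**The case against.** Four stronger readings are tempting, and the documents do not support them.

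- *A reader might infer that the protocol's odds ratios would have been adjusted for BCVA and age.* The adjustment sentence concerns the tree and names no confounder. The protocol's final logistic regression, the method tied to the odds-ratio summary measure, is described with imaging variables only. On that step the SAP matches the protocol.
- *A reader might infer that the unadjusted odds ratios are biased.* The clinical question is which early parameters could predict response, and a marker correlated with BCVA still predicts. Neither document sets incremental value over the letter score as an objective.
- *A reader might infer that the change of method was hidden.* Dropping RECPAM is declared, with reasons and a pointer to Section 6.3.1, where every candidate is listed. Only the fate of the adjustment is left unstated.
- *A reader might infer that baseline BCVA drives the outcome.* BCVA is an and/or input, assessed at Week 16 and later visits. Baseline BCVA is at most a proxy for it.

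Two further objections stand. Protocol Section 1.1 describes the CNV abnormalities as leading to photoreceptor loss and reduced vision, so BCVA may be a consequence of the anatomy, and adjusting for it could remove real anatomical signal. And 122 patients leave little room for extra terms. Both limit how the adjusted model can be used and read. Neither removes the gap in Section 1.1 or the usefulness of a side-by-side report.

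**Conclusion.** The point holds in a limited form. The protocol committed the tree step to confounder adjustment; the SAP removed that step, did not say what became of the adjustment, and left every outcome model with imaging variables only. The odds ratios can be reported as unadjusted predictive associations, but not as evidence that a marker adds to baseline BCVA and age.

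The possible effect runs from negligible (odds ratio 0.88, 0.4 SE) to material (0.54, 1.7 SE). This range rests wholly on the assumed inputs, and the direction is assumed too. The shortcut exp(−ln 2.0) = 0.50, or 0.693/0.36 = 1.9 SE, overstates the extreme because it ignores averaging over BCVA within each marker group. The change is worth making because it is cheap and serves the trial's stated purpose; the primary model is not invalid without it.

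**What to change.** 1. **SAP 6.3.1:** leave the primary model as it is. Add a prespecified sensitivity analysis that refits the final multivariable model with baseline BCVA (continuous) and age forced in. Fit both versions on the same patients and report the marker odds ratios with 95% confidence intervals side by side.
2. **Interpretation, stated in advance:** if an odds ratio moves towards 1 on adjustment, read this as lack of incremental value over BCVA and age, not as proof of confounding, because BCVA may itself follow from the anatomy.
3. **SAP 1.1:** add one sentence saying that the protocol's confounder adjustment within RECPAM is carried over only as this sensitivity analysis. If the refit is not adopted, state instead that the adjustment is dropped and that the odds ratios are unadjusted.

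Cost: one more model fit and one more table. Age is collected at Screening and BCVA at Baseline, so no new data are needed. The real price is two more coefficients where the protocol's own rule allows about 5 to 6, which leaves about 3 to 4 for imaging. The adjusted model should therefore be labelled exploratory, or fitted with penalised estimation if many imaging terms are retained.

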12.4.3 Handling of remaining intercurrent events of primary estimand

As described in [Table 12-1](#), participants who prematurely discontinued the study should be considered a not q12w fluid-free at Week 48.

12.4.4 Handling of missing values not related to intercurrent event

Imputation of missing values will be done following the Last Observation Carried Forward (LOCF) method mainly for the secondary endpoints. An observed approach will be also considered.

12.4.5 Sensitivity analyses for primary endpoint/estimand

A sensitivity analysis on the primary model will be performed using the LOCF approach in case of missing SD-OCT or OCTA evaluations between Week 4 and Week 16.

12.4.6 Supplementary analysis

Not applicable.

12.4.7 Supportive analyses

To investigate the robustness of the primary analysis with respect to a potential selection bias due to dropouts, the following approach will be used: a weighted multivariable logistic regression will be applied to provide a robust inferential procedure for the analysis of predictors of patients' responses in presence of missingness. Since excluding participants because of missing values could introduce a selection bias, in order to restore the complete-case analysis to its

original sample representation, each complete participant will be weighted for the inverse of his/her missingness probability (evaluated by means of a logistic regression considering all baseline available covariates and the dropouts during the one-year period as response variables) (Höfler et al., 2005).

Further details will be provided in the Statistical Analysis Plan (SAP).

12.5 Analysis of secondary endpoints

12.5.1 Efficacy and/or Pharmacodynamic endpoint(s)

All secondary efficacy analyses will be based on the FAS. The analyses performed at eye level will focus on the study eye only.

The secondary efficacy objective and endpoints of this study are as follows:

To evaluate the effect of brolucizumab on the evolution of qualitative and quantitative OCTA parameters of wAMD from Baseline to Week 48

Summary statistics of each parameter assessed by OCTA, of which the main quantitative parameters are CNV flow size and vessel density, and the main qualitative ones are branching vessels, peripheral anastomotic arcades, vascular loops and dark halo, from Baseline up to Week 48 will be provided, including changes vs Baseline. Paired t-test or Wilcoxon signed rank test, based on data distribution, will be used to test the difference at each time point vs Baseline for continuous parameters. In case of a dichotomous parameter, a McNemar test will be used.

To evaluate the effect of brolucizumab on the evolution of qualitative and quantitative SD-OCT parameters of wAMD from Baseline to Week 48

Summary statistics of each parameter assessed by SD-OCT, of which the main quantitative parameters are CRT and PED volume, and the main qualitative ones are IRF, SRF, sub-RPE fluid, status of ELM, SHRM and outer retinal tubulation, from Baseline up to Week 48 will be provided, including changes vs Baseline.

Paired t-test or Wilcoxon signed rank test, based on data distribution, will be used to test the difference at each time point vs Baseline for continuous parameters. In case of a dichotomous parameter, a McNemar test will be used.

To evaluate the effect of brolucizumab on the evolution of functional parameters of wAMD from Baseline to Week 48

Summary statistics of BCVA from Baseline at each visit up to Week 48 as well as changes vs Baseline will be provided. Paired t-test or signed rank test, based on data distribution, will be used to test the difference at each time point vs Baseline.

Frequency of patients with an improvement of at least 5/10/15 letters or worsening will be also provided.

To evaluate the effect of brolucizumab on sustained dryness from Baseline to Week 48

- Time to reach sustained dryness of the study eye, as defined by the absence of IRF and SRF for at least 2/3 consecutive visits, will be descriptively summarized. Survival Kaplan-Meier curve will also be provided including summary estimates.

- Summary statistics of cumulative incidence of sustained dryness of the study eye will be provided by means of absolute and relative frequencies of participants with sustained dryness as defined above at each timepoint from Week 8 to Week 48. The binomial proportion and 95% confidence interval (CI) using the Clopper-Pearson method will also be provided.

To evaluate the reasons underlying the Investigators' choice of brolucizumab treatment regimen (q21w or q8w) at Week 16

The reasons underlying the Investigator's choice of brolucizumab dosing regimen (q12w or q8w) at Week 16 among BCVA and/or IRF, SRF, sub-RPE fluid, hemorrhage and/or CRT and/or OCTA parameters and/or 3-field CFP will be descriptively summarized. A multivariate logistic regression model will also be implemented in order to evaluate which of these factors are determinants for the selection of the dosing regimen at Week 16.

Further details will be provided in the Statistical Analysis Plan (SAP).

